feedback to obtain baseline adherence. If the participant did not bring their inhalers to the appointment, a coordinator will follow up with the patient to ensure that the Propeller or FindAir sensors are properly attached to the patients' inhalers. In addition, all participants receive a mobile spirometer (Spirobank Smart) to track their lung function throughout the study. The spirometer connects to an app (Propeller or FindAir) via Bluetooth. This app allows the participant to perform pulmonary function tests (PFTs) and view the results of these tests, such as their forced expiratory volume (FEV1) as well as other lung function parameters. Participants will be asked to use the spirometer at least once a month when completing study visits over the phone with a study team member. Following the baseline visit, a 8 week run-in phase will be completed to assess baseline adherence using electronic inhaler monitoring. After 4 weeks in baseline, the coordinator will call the participants in TASC and TAU for their first monthly phone call. After obtaining 8 weeks of baseline adherence data, the coordinator will call the participants in TASC and TAU for their second monthly phone call. The coordinator will calculate baseline adherence and obtain data for the Composite Asthma Severity Index (CASI) and the Asthma Control Test (ACT) for TASC and TAU participants. For TASC participants only, the coordinator will introduce Step 1 of the intervention for all participants. Adherence checks will continue to occur every four weeks for the duration of the study for all participants and adherence <68% will prompt movement from one level of treatment to the next for TASC participants only. The study coordinator will calculate the participant's adherence percentage prior to the monthly telephone call. During the call, the coordinator will tell the participant if they will get moved up to the next step and explain what they will be doing during that step. TASC participants may remain at a treatment level for more than four weeks and may complete 1, 2, or 3 interventions steps during the 5 month study depending on the adolescent's adherence.

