Brief measures will be completed by patients online via REDCap. Participant specific data such as asthma severity, lung function, and adherence will be collected through the Propeller Health or FindAir mobile phone application, TreatSmart web portal, and via telephone. Clinical chart reviews will be conducted by study staff to provide an accurate estimate of lung function and disease severity from the date of consent to the end of study date.

Adherence Assessment:

Medical chart reviews will be conducted by study personnel to obtain information on medication regimen.

- **Electronic Monitoring:** The Propeller Health or FindAir monitoring system includes a Bluetooth enabled sensor that attaches to the patient's inhaler. This sensor records every dose, or "puff", the patient takes and sends it to a corresponding online database that is accessible to study staff. All participants will be given this sensor at baseline. Patients will not receive medication adherence feedback during the first month of the study as baseline inhaler adherence data will be collected during this time. TASC participants who move into Step 2 of the intervention will have access to their adherence via the Propeller Health or FindAir application. Study staff will have

PROTOCOL TITLE: Using Technology- Assisted Stepped Care Intervention to Improve Adherence in Adolescents with Asthma

access the patient's adherence from a daily, weekly, and monthly standpoint through the Propeller Health or FindAir provider portal.

- **Adolescent Barriers to Medication Scales (AMBS):** The AMBS is an 18-item validated measure of perceived barriers to medication adherence in adolescents. The wording will be modified slightly to match asthma treatment regimens. Good internal consistency and construct validity have been documented. The participant's AMBS score will be obtained at the baseline visit via REDCap questionnaire and again via phone at the end of the study.
- **Asthma Responsibility Questionnaire (ARQ):** A brief validated measure that assess patterns of family responsibility for asthma management and the division of family responsibility for 10 asthma management tasks. Good internal consistent and convergent validity have been documented⁸⁴. Participants will complete the ARQ at the baseline visit via REDCap and again at the end of the study via phone.

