- **COVID-19 and Learning Questionnaire:** A brief set of questions that assesses the current learning environment and its consistency to evaluate the impact on adherence. The participants' responses will be obtained verbally and recorded in an excel database. At each of the subsequent study visits, the study coordinator will check-in with participants to see if there have been any changes to their school schedule since their previous visit.

Lung Function Assessment:

- **MIR Spirobank Smart™:** The mobile spirometer records multiple parameters of the patient's lung function including FEV1 (forced expiratory volume), PEF (peak expiratory flow), FVC (forced vital capacity), FEV1/FVC ratio, FEV6, and FEF2575 (forced expiratory flow). The spirometer sends the FEV1, PEF, FVC, FEV1/FVC, FEV6, and FEF2575 values to the corresponding mobile phone application, Propeller Health or FindAir, which is directly accessible to the patient. Other values will be accessible to study staff through a secured database. Participants will be able to view their previous lung function data as well as adherence data within the phone application. Participants will also be asked to use their spirometer while on the phone with the study coordinator during their monthly visits.

Disease Severity Assessment:

- **Composite Asthma Severity Index (CASI):** The participants' CASI score will be calculated through the TreatSmart program on a CCHMC secured laptop. The TreatSmart software web-based program, developed at CCHMC and hosted on a CCHMC secure server, will be used to determine the participant's symptom burden, health care utilization, systemic corticosteroid use, and current medication use to determine the level of asthma severity/control the participant has. The study coordinator will collect this information from the participant at baseline and then once a month during the study telephone call and will enter the data into the program. The program also makes an initial treatment recommendation based on the National Asthma Education and Prevention Program (NAEPP asthma guidelines) if the

PROTOCOL TITLE: Using Technology- Assisted Stepped Care Intervention to Improve Adherence in Adolescents with Asthma

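### The coordinator who knows the arm and announces step changes also collects CASI and ACT in the same monthly call, which can bias the secondary outcome and can be cheaply reduced

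*Combined protocol and SAP*

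**What the plan says.** All of this is in Section 6.0 (Procedures Involved) unless noted.

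- **Adherence.** "The study coordinator will calculate the participant's adherence percentage prior to the monthly telephone call". Adherence checks cover both arms, but the rule acts in one: "adherence <68% will prompt movement from one level of treatment to the next for TASC participants only".
- **Step delivery.** "During the call, the coordinator will tell the participant if they will get moved up to the next step". At the second monthly call, "For TASC participants only, the coordinator will introduce Step 1 of the intervention". The coordinator therefore knows the arm by that call at the latest.
- **CASI.** "The study coordinator will collect this information from the participant at baseline and then once a month during the study telephone call". The coordinator enters the answers, and the "CASI score will be calculated through the TreatSmart program on a CCHMC secured laptop".
- **ACT.** It consists of the participant's own ratings, taken by telephone each month. The coordinator's part is explicit at the second monthly call, which is to "obtain data for the Composite Asthma Severity Index (CASI) and the Asthma Control Test (ACT) for TASC and TAU participants".
- **Self-completion.** It is already in use for other instruments: "Brief measures will be completed by patients online via REDCap".
- **Chart review.** Study staff are to review charts for lung function and disease severity from consent to study end. Whether they are blinded is not stated.

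Section 17.0 makes change in CASI the secondary outcome, tested by ANCOVA. Section 6.0 places the primary endpoint at post-treatment, which is Visit 7 at 6 months in the schedule of measures. Neither section mentions blinding of outcome assessors or the order of tasks within a call.

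**The concern.** CASI depends on what the participant says about symptoms, health care use, steroid courses and medication, and on how the interviewer asks and records it. An interviewer who knows the arm may probe or code differently in the two arms without intending to. In interim calls a TASC participant may also hear about a step change before answering symptom questions, which never happens to a TAU participant.

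Measurement error that is the same in both arms costs precision. Error that differs by arm shifts the estimated treatment effect, and adjustment for baseline in an ANCOVA does not remove it. What is at stake is the reading of Hypothesis 2, and any CASI effect size carried forward to a later efficacy trial.

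**Working it through.** **1. Which mechanism applies at which call**

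| Call | Arm known to coordinator | Step news possible |
|---|---|---|
| Month 1 | Not settled (randomization follows the baseline measures) | No |
| Month 2 | Yes | Step 1 introduced, TASC only, whatever the adherence |
| Months 3 to 5 | Yes | Yes, TASC only, driven by adherence |
| Month 6 (post-treatment) | Yes | None should remain to announce |

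At the endpoint the operative issue is knowledge of arm. The step announcement bears on the interim calls. It also bears on the 2-month call if that call supplies the baseline CASI. The plan does not say whether baseline for change is Visit 1 or the end of the run-in.

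**2. The plan's own figure**

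Section 17.0 gives power of at least 0.80 for d of 0.72 or more, for Hypothesis 1 only. In the conservative corner of its assumptions, 60 participants less 20% attrition leave 24 per arm, and R-squared is 0.20. I assume a two-sided 0.05 test, because sidedness is not stated for this hypothesis.

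- Residual SD = √(1 − 0.20) = 0.894
- z = 0.72 / (0.894 × √(2/24)) = 2.789
- Power = Φ(2.789 − 1.960) = 0.796

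The stated figure reproduces. A noncentral t with three covariates gives 0.778. No SD, effect size or power is given for CASI, so this figure neither supports nor weakens the point.

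**3. Illustration of sensitivity**

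Suppose there is no true CASI effect and recorded CASI differs between arms by b SD (unadjusted) because of how it was collected. With n per arm:

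- Noncentrality = b / √(1 − R²) × √(n/2)
- Degrees of freedom = 2n − 2 − 3
- Example: n = 30, R² = 0.20, b = 0.2 gives 0.2 / 0.894 × √15 = 0.866. The critical value on 55 degrees of freedom is 2.004, and the rejection probability is 0.136.

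| Analysed | R² | b = 0.1 | b = 0.2 | b = 0.3 |
|---|---|---|---|---|
| 48 | 0.20 | 0.067 | 0.118 | 0.206 |
| 48 | 0.40 | 0.072 | 0.141 | 0.259 |
| 60 | 0.20 | 0.071 | 0.136 | 0.248 |
| 60 | 0.40 | 0.078 | 0.166 | 0.314 |
| 80 | 0.20 | 0.078 | 0.167 | 0.316 |
| 80 | 0.40 | 0.088 | 0.207 | 0.401 |

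With b = 0 every entry is 0.050. Every b is an assumption. The R-squared range is borrowed from the adherence power calculation. 80 is the recruitment ceiling, so that row is an upper bound on the number analysed.

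**The case against.** The strongest reply has five parts.

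- **Scoring is automated.** TreatSmart computes CASI, and ACT is the participant's own rating. This stands against any reading that the coordinator scores CASI. It does not protect the answers that are elicited and entered.
- **Knowing adherence is not in itself a difference between arms.** The percentage is calculated in both arms, so an expectation tied to low adherence differs by arm only if adherence does. This stands; the between-arm issue is knowledge of arm.
- **Hiding the current percentage achieves little.** Staff have daily, weekly and monthly portal access, and the coordinator knows earlier results and the current step. This largely stands. The gain comes from taking interviewer discretion out of the symptom items.
- **A mid-study change has costs.** Version 10.0 follows revisions since 2019, which suggests a trial under way, although no enrolment dates are given. Moving from telephone to REDCap could mix modes across participants or between baseline and follow-up. This stands and shapes the fix.
- **Other evidence exists.** Chart review is planned, Section 2.0 also lists mobile spirometry under Hypothesis 2, and this is a feasibility trial. These limit the consequence but do not protect CASI.

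A reader might infer that the secondary outcome is biased, that ACT is a secondary outcome too, or that step news contaminates the endpoint. The documents support none of these. They show exposure without size or direction, Section 17.0 names only CASI as secondary, and no further step should remain to announce at the last visit.

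**Conclusion.** The point holds as a risk to CASI, not as a demonstrated bias. One role knows the arm, delivers the steps and collects the CASI inputs, with nothing in the plan to separate these tasks. The primary outcome is recorded by sensor and does not pass through this interview.

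The size cannot be estimated from the documents. For 48 to 80 analysed and R-squared 0.20 to 0.40, an assumed shift of 0.1 SD gives a false-positive rate of 0.067 to 0.088, and 0.2 SD gives 0.118 to 0.207. These figures show only that small arm-related shifts matter at this sample size. They also attribute the whole shift to the interviewer, whereas part could come from participants who know their arm. I class this as a cheap improvement worth making.

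**What to change.** In both arms and at every visit including the last:

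1. Record ACT and the CASI symptom items first, and save them before the adherence percentage is opened or any step is discussed. Use participant self-completion in REDCap or, to avoid mixing modes for those already enrolled, a fixed script read verbatim.
2. Use the chart review already planned to check the utilization, steroid and medication inputs to CASI.
3. State which visit supplies the baseline CASI.
4. State as a limitation that assessors are not blinded, and that reporting bias from unblinded participants is not removed.

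The costs are modest. The adherence calculation moves to after these items are saved, so the Section 6.0 sentence on its timing needs rewording. REDCap answers must be entered into TreatSmart, and some participants will need reminders. Any change of mode part-way through must be dated, recorded and applied equally in both arms. Sample size, alpha, power and the step rule are unchanged. No need for extra staff is apparent, though the documents do not settle that.

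Under the assumptions above, if the fix halved a 0.2 SD shift, the false-positive rate at 60 analysed and R-squared 0.20 would fall from 0.136 to 0.071. The halving is itself an assumption.

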7.0 Data and Specimen Banking

Not applicable.

8.0 Sharing of Results with Subjects

The results will not be shared with the participant's primary care physicians.

9.0 Study Timelines

PROTOCOL TITLE: Using Technology- Assisted Stepped Care Intervention to Improve Adherence in Adolescents with Asthma

Participants will be enrolled in the study for a duration of 6 months. It is anticipated that all participants will be enrolled at the end of the 5th year of the study. It is anticipated that primary data analyses will be completed a year after study enrollment is complete.

10.0 Inclusion and Exclusion Criteria

Eligible adolescents will be identified through electronic medical records and recruited during outpatient medical visits or via telephone. Adolescents with a history of nonadherence per physician report will be targeted.

Inclusion Criteria:

- Patient age between 12-18 years
- Patient is diagnosed with severe-persistent or moderate-persistent asthma per NAEPP asthma guidelines
- Patient is prescribed at least one daily inhaled controller medication or a daily combination inhaled corticosteroid and long-acting beta-agonist and a beta-agonist bronchodilator
- English fluency for patient, caregiver, and clinician

Exclusion Criteria:

- Significant cognitive deficits that may interfere with comprehension per medical team or chart review
- Diagnosis of serious mental illness (e.g., schizophrenia)
- Diagnosis of pervasive developmental disorder
- Active chronic disease apart from asthma or allergic disease (e.g. Bronchiectasis, pulmonary hypertension, and moderate or severe tracheomalacia)
- Patient receives school administered daily controller medication at the time of the enrollment visit

11.0 Vulnerable Populations

This study includes vulnerable subjects (children). Our research team has extensive experience with the unique needs of this population, thus this study presents minimal risk to patients, no greater than those encountered in routine behavioral assessment and clinical care. There are no medical risks. The assessments are similar to tasks conducted in our outpatient clinics. Intervention sessions will utilize evidence-based strategies similar to those conducted clinically in outpatient clinics. It is possible that participants may feel uncomfortable responding to questions about their adherence, social support, medication knowledge, problem-solving or barriers to adherence, asthma responsibility, or behavioral difficulties. All participants will be reminded that they can decline to answer any questions if they choose without negative repercussions. The PI, [name] is a licensed Clinical Psychologist and will be available to participants at any time during study participation. Consistent with HHS regulations for minimal risk studies, adolescent assent and parental consent will be obtained. Trained study staff will obtain-age appropriate written information consent/assent. All pertinent aspects of

PROTOCOL TITLE: Using Technology- Assisted Stepped Care Intervention to Improve Adherence in Adolescents with Asthma

consent/assent will be reviewed verbally and in writing including study purpose, risks/benefits, confidentiality, and right to withdraw. Patients will be informed that their care at CCHMC will not be affected whether they choose to participate in the study and that they are able to withdraw at any time. Study staff will address all questions and concerns. No assessment procedures will occur until after parent consent and adolescent consent or assent are obtained.

12.0 Local Number of Subjects

Up to 80 adolescents will be enrolled in the current study.

13.0 Recruitment Methods

Adolescents will be recruited through the CCHMC Asthma Center, which conducts 4500 patient visits each year. Eligible adolescents will be identified through electronic medical records and approached during outpatient medical visits. Adolescents with a history of nonadherence per physician report will be targeted. Study staff will meet with interested adolescents and parents to confirm eligibility and obtain written consent/assent.

Adolescents may also be recruited via telephone. For the patients study staff plan to recruit via phone, a recruitment letter will be mailed or emailed to eligible families with upcoming pulmonary appointments, which will describe the study briefly and include an “opt out” phone number to call if they do not wish to be contacted about the study. Two weeks after sending the letters, study staff will call potential participants to discuss the study more thoroughly. Reasons for decline and sample composition will be tracked throughout the study to ensure accurate representation and to examine the reach of the intervention based on the enrollment rate of high-risk or underserved individuals.

Participants will be compensated for their participation in the amount of \$50 for the baseline assessment, \$20 at the end of month 1, \$20 at the end of month 2, \$25 at the end of month 3, \$30 at the end of month 4, \$40 at the end of month 5, \$75 at the end of the study. In addition, participants will be paid \$10 a week for syncing their Propeller or FindAir caps in conjunction with the Step 2 texting intervention, allowing the interventionists to obtain the data needed to complete the intervention. Participants who qualify for behavioral intervention sessions will be paid \$15 per session for up to four sessions. In the event that a study phone is not returned, we will attempt via phone and email to reach the family and set up a way to retrieve it in person or via mail. Given the high cost of the phones, if, after several months it is still not returned, we may offer an incentive of \$50 for the safe return of the working mobile device, no questions asked.

Families will be compensated using a reloadable debit card (ClinCard). The ClinCard will be given to families at the initial visit and compensation will be loaded once their initial visit is complete. In addition, families will receive a handout with instructions on how to use the debit card (Appendix 19.B - ClinCard Debit Card handout). Families are encouraged to keep their debit card for future visits but, should they need another card, it will be provided to them at no cost. Cards will be loaded by research coordinators immediately after a visit is completed.

14.0 Withdrawal of Subjects

Participants may withdraw from the study at any time and will be informed of this right verbally and in writing during the consent process. The principle investigator may remove participants from the study for abuse of CCHMC device privileges (see cell phone contract).

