6.0 Procedures Involved

The current study involving human subjects consists of a Randomized Controlled Trial to test the feasibility, effectiveness, and implementation of the TASC intervention as compared to a treatment as usual group. A total of up to 80 adolescents with moderate or severe persistent asthma between the ages of 12-18 years will be randomized to TASC (n=35) or treatment as usual (n = 35). After adolescent participants have met inclusion criteria, completed baseline assessments, and have been enrolled in the feasibility RCT, they will be randomized to either TASC or Treatment As Usual (TAU). The statistician will make the randomization schedule and the principle investigator will maintain randomization schedule. Outcomes measures (adherence and disease severity) will be assessed at baseline, monthly during active treatment, and at post-treatment, with the primary endpoint being post-treatment.

Participants will be enrolled in the study for a duration of six months. First, participants will complete baseline questionnaires related to demographic, and clinical predictors of adherence and asthma. Participants will be randomized following completion of baseline measures. A smart phone prepared by the CCHMC IT team with a data plan will be provided to participants who do not have their own cellphone. Propeller or FindAir adherence caps will also be provided to all participants and utilized for 2 months without

PROTOCOL TITLE: Using Technology- Assisted Stepped Care Intervention to Improve Adherence in Adolescents with Asthma

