- **Credibility/Expectancy Questionnaire (CEQ):** A brief, 6-item validated measure of treatment credibility and outcome expectancy. The wording of the items will be modified slightly for the current intervention, but the format and response options will remain the same. Internal consistency and test-retest reliability of the CEQ range from .75- .85⁸⁵. Participants will complete the CEQ via phone at their second visit.

Implementation:

- **Implementation:** Treatment fidelity and time needed for the intervention will be assessed. Treatment fidelity will be assessed through fidelity checklists created specifically for each intervention session. Sessions will be timed and the number of weeks to complete the session will be tracked to determine the average length of time needed for the intervention.
- **Reach:** Enrollment rate of high-risk or underserved individuals, reasons for declining participation, and representativeness of the sample will be assessed and monitored
- **Potential for Sustainability:** Process evaluation regarding the facilitators/barriers to delivering TASC intervention, possible facilitators and barriers for sustaining intervention after study completion, and feedback regarding intervention changes that could improve adoption or sustainability.
- **Perceived Characteristics of Intervention Scale (PCIS):** 19 item measure of interventionist's views toward the study intervention. This questionnaire will be completed at the end of the study.

	Baseline (in person or via phone)	Follow up (via phone)	Follow Up (via phone)	Final Visit (via phone)			
Measures	Visit 1	Visit 2 (1 month)	Visit 3 (2 months)	Visit 4 (3 months)	Visit 5 (4 months)	Visit 6 (5 months)	Visit 7 (6 months)
Electronic Monitoring	X	X	X	X	X	X	X

PROTOCOL TITLE: Using Technology- Assisted Stepped Care Intervention to Improve Adherence in Adolescents with Asthma

AMBS	X						X
ARQ	X						X
COVID Questionnaire	X	X	X	X	X	X	X
Mobile Spirometry	X	X	X	X	X	X	X
CASI	X	X	X	X	X	X	X
ACT	X	X	X	X	X	X	X
BASC-3	X						X
Knowledge Questionnaire	X						
Hardship Questionnaire	X						
ACTA	X						
TENS-Task	X			X			
TENS-Interface	X			X			
TENS- Life	X			X			
Feasibility Step 1				X			
Feasibility Step 2*					X	X	X
Feasibility Step 3*						X	X
Acceptability Questionnaire							X
SUS*				X	X	X	X
AIM							X
IAM							X
FIM							X
CEQ			X				

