Many procedures are in place to guard against missing or unusable data; however, missing data are almost inevitable in clinical research. The strategy for accommodating missing values is to first investigate and identify patterns of missingness, by group and variable, by using established pattern identification techniques. To the extent possible, potential mechanisms of missingness will be identified, including values deemed to be missing at random, completely at random, or not random at all. If substantial missing data are observed, parameter estimation using multiple imputation methods will be computed to estimate the missing values, and relevant predictors related to missingness will be added to our models. Sensitivity analyses will be conducted, with and without outliers/extreme values, and with and without imputed values to test the stability of our models under alternative conditions.

PROTOCOL TITLE: Using Technology- Assisted Stepped Care Intervention to Improve Adherence in Adolescents with Asthma

All data will be de-identified with the use of unique assigned study identifier codes. All electronic data will be stored on a CCHMC network server with built-in security. Treatsmart program data and web-based databases are located on a CCHMC secure server. Propeller Health or FindAir adherence data is located on their HIPAA-compliant servers and will be transferred securely to the CCHMC investigators at the end of the study for data analysis. Smartphones provided by CCHMC for use by the participants in the clinical study will be loaded with a security software program, Air Watch. Air Watch is a mobile device management technology that enables IT to deploy, configure, manage, support, and secure mobile devices from afar to provide remote configuration, troubleshooting, and lock and wipe security. Air Watch will not be loaded on participants' personal cell phones.

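### Section 14.0 lets the principal investigator, who keeps the randomisation schedule, remove randomised participants for device abuse, with no rule for their follow-up, data or analysis

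*Combined protocol and SAP*

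**What the plan says.** **The removal rule.** Section 14.0: "The principle investigator may remove participants from the study for abuse of CCHMC device privileges (see cell phone contract". It is a permission, not a requirement, and it names one decision-maker. Any criteria would be in the contract, which is not among the documents.

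**Who knows the allocation.** Section 6.0: "The statistician will make the randomization schedule and the principle investigator will maintain randomization schedule". The same section places randomisation after the baseline measures and before the end of the eight-week run-in.

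**Who holds a hospital device.** Section 6.0: "A smart phone prepared by the CCHMC IT team with a data plan will be provided to participants who do not have their own cellphone". Section 17.0 describes remote management, including locking and wiping, for study phones and adds: "Air Watch will not be loaded on participants' personal cell phones". Other equipment goes to everyone. Section 6.0 says "Propeller or FindAir adherence caps will also be provided to all participants" and gives every participant a mobile spirometer.

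**Other discontinuation rules.** Section 18.0 and the Data Safety and Monitoring Plan in the appendix (section 28.0) list family request and the investigators' judgement of the patient's health. Section 19.0 lists family request and a significant adverse event. None mentions device abuse.

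**Analysis.** Section 17.0 names ANCOVA for Hypotheses 1 and 2. It plans multiple imputation if missing data are substantial, with sensitivity analyses with and without imputed values. It states no analysis population and sets no threshold for substantial.

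**The concern.** A randomised comparison is protected by keeping everyone randomised in follow-up and in the analysis. Section 14.0 opens an exit that has nothing to do with safety, eligibility or the family's wishes. It is used at the discretion of someone who can know the participant's arm, and mostly after randomisation. Removal from the study, in its ordinary meaning, ends later outcome collection.

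The rest of the plan does not close the gap. There is no instruction to keep following a removed participant, to retain what was already collected, or to analyse that participant in the assigned arm. A handful of removals might not count as substantial missing data, and the default would then be a comparison of those who remained.

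Removal also gives up outcomes that do not depend on a loaned phone. Section 6.0 collects CASI and ACT in telephone calls and runs chart review from consent to the end of the study. There is a secondary interest too. Adolescents without a phone may overlap with the groups whose reach Aim 2 examines: "Enrollment rate of high-risk or underserved individuals, reasons for declining participation, and representativeness of the sample will be assessed and monitored".

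**Working it through.** **1. The plan's own figure.** Section 17.0 gives power of at least 0.80 for d ≥ 0.72 with 60 participants, alpha 0.05, covariate R² of 0.20 to 0.40 and attrition of 0 to 20%. The assumed pre-post correlation is not given, so the Monte Carlo runs cannot be repeated exactly. A normal approximation (two-sided, 1:1, n per arm) is

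power = Φ( d/√(1−R²) × √(n/2) − 1.96 )

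- Worst stated case: 60 less 20% is 48, so n = 24, with R² = 0.20. Then 0.72/0.894 × √12 = 2.79, and Φ(0.83) = 0.796.
- Best stated case: n = 30, R² = 0.40. Then 0.72/0.775 × √15 = 3.60, and Φ(1.64) = 0.950.

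A noncentral-t version with three covariates gives 0.778 and 0.943. The stated figure is reproduced closely enough to serve as a baseline.

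**2. How many removals.** The documents give neither the share of participants lent a phone nor a removal rate. Assumed: 10 to 30% of 80 borrow a phone, and 5 to 15% of borrowers are removed.

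- Borrowers: 80 × 0.10 = 8, to 80 × 0.30 = 24.
- Removals: 8 × 0.05 = 0.4, to 24 × 0.15 = 3.6, so about 0 to 4.
- Each removal is 1/80 = 1.25% of those recruited, or 1/60 = 1.7% of those needed for Hypothesis 1.

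**3. Effect on power.** Take 80 enrolled, 20% attrition, then further removals (noncentral t, d = 0.72):

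| Further removed | N left | Power, R² = 0.20 | Power, R² = 0 |
|---|---|---|---|
| 0% | 64.0 | 0.886 | 0.809 |
| 2.5% | 62.4 | 0.878 | 0.799 |
| 5% | 60.8 | 0.869 | 0.788 |
| 10% | 57.6 | 0.850 | 0.766 |

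Even 10% costs only about four points. Power is not the issue.

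**4. Effect on bias.** Let p be the proportion removed in an arm and D the gap, in SD, between the means of those retained and those removed. The full-arm mean is the retained mean minus pD, so a complete-case mean is shifted by pD. With the same D in both arms,

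bias = (p_TASC − p_TAU) × D

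Assume 40 per arm and D = 0.5 to 1.0:

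- Equal removal: 0.
- Mid-range: 80 × 0.20 × 0.10 = 1.6 removals, split 2:1 towards TASC. That is 1.07/40 − 0.53/40 = 1.3 percentage points, and a bias of 0.007 to 0.013 SD (about 1 to 2% of d = 0.72).
- Extreme: 4 removals, all in TASC (10% against 0%), giving 0.05 to 0.10 SD (7 to 14% of d = 0.72).

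A split towards TAU reverses the sign.

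**The case against.** The case for leaving the rule alone has several parts.

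- **Removal may be rare or a last resort.** The text is permissive, and the unseen contract may provide for warnings or loss of the phone first. Section 13.0 is lenient about unreturned phones. This stands: the documents do not show that misuse must lead to removal, or that removal is the only sanction. They do permit it.
- **A reader might infer that removed participants' outcomes are discarded.** No section says so. Section 6.0 makes no exception to chart review for removed participants, and section 17.0 plans for missing data. What is established is that follow-up after removal and the fate of collected data are unspecified.
- **A reader might infer that only adolescents without their own phone can be removed.** The contract's name makes that likely, but the stated ground is hospital device privileges, and caps and spirometers go to everyone.
- **Custody of the schedule adds little.** TASC is visibly different from usual care, and the principal investigator oversees all study components (section 15.0) and reviews study data weekly (section 18.0). The arm could be known anyway. This stands as to the schedule alone, but it leaves a discretionary exclusion by someone who can know the allocation.
- **A reader might infer that removals flatter TASC**, because TASC uses phones for more of its content. More use does not imply more abuse. Borrowers in both arms need a phone for the sensor and spirometer app, and nonadherent adolescents are targeted throughout. The direction is not shown.
- **A reader might infer that Aim 2 will misstate reach.** Section 13.0 tracks sample composition throughout the study, which limits this.

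**Conclusion.** The point holds as a modest defect that is cheap to correct. Section 14.0 permits a discretionary, non-clinical exclusion of randomised participants by the person who maintains the schedule. No intention-to-treat population, follow-up rule or data-retention rule limits its effect, and the ground is missing from the other discontinuation rules.

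The likely size is small: about 0 to 4 removals, and a complete-case bias from zero to about 0.01 SD in equal-removal or mid-range scenarios. A bias of 0.05 to 0.10 SD requires every removal at the upper end of the range to fall in one arm. These figures rest on assumed borrowing rates, removal rates and outcome gaps, and on 40 participants per arm. The sign of any bias is open. The reason to act is that the exclusion is avoidable, not that it is likely to change the result.

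**What to change.** Amend section 14.0, and the cell phone contract to match, so that device abuse may lead to withdrawal of the loaned device, by remote lock with the Air Watch software already installed, but not to removal from the study. State that the participant:

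- stays in the assigned arm and keeps all data already collected;
- continues CASI and ACT calls on any available telephone, and chart review, to month 6;
- syncs the inhaler caps through another phone, such as a caregiver's, where one is available;
- is analysed as randomised.

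Add to section 17.0 that the analysis population is everyone randomised, and that device withdrawals are reported by arm. Reporting by arm matters because the decision to withdraw a device could itself differ between arms. Reconcile section 14.0 with sections 18.0, 19.0 and the appendix, so that the grounds for ending participation agree.

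The cost is a few sentences, using calls, chart review and software already in the plan. The main downside concerns the primary outcome: an adolescent with no other phone may have incomplete sensor data, and in TASC may lose a delivery route for the intervention. Full removal would lose both as well, along with the telephone outcomes.
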